### **Dry Time**

- Dry time down to the closest measure in seconds will be summarized using a mean and standard deviation and will be compared across groups with post-hoc comparison tests. Total time with glue time, mesh time, and dry time will be summarized using a mean and standard deviation.

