## **8 STATISTICAL CONSIDERATIONS**

### **8.1. Sample Size Determination**

The purpose of this study is to show non-inferiority between the two products. We are reporting superiority results, as the noninferiority results were indeterminate. A sample size of 30 per incisional length group was estimated based on the secondary outcome of difference in mean “Dry Time” using estimated means (no standard deviations) from the vendor for both OptiClose and Competitor product, and estimation of effect size. The comparison will be made using a one-sided, two-sample unequal-variance t-test, with a Type I error rate ( $\alpha$ ) of 0.025. The standard deviation for Group 1 is assumed to be 0.01 and the standard deviation for Group 2 is assumed to be 0.01. With sample sizes of 15 in OptiClose Product and 15 in Dermabond, and with 90% power, the corresponding detectable difference in means is 0.02226. Provided exact standard deviations, an exact difference can be adjusted accordingly. The detectable difference was computed using PASS 2024, version 24.0.2.

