### **Number of Applicator Tubes**

- A Chi-Square test will be used to compare the observed frequencies of number of tubes between the two products. The test statistic is calculated by comparing the observed frequency to the expected frequency under the null hypothesis. The p-value will be obtained to determine the statistical significance of the observed difference.

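### Section 8.8.2 does not specify the Welch test of dry time on which section 8.1 sizes the trial, so power under the planned analysis is undefined

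*Combined protocol and SAP*

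**What the plan says.** Section 8.1 makes dry time the sizing outcome: "A sample size of 30 per incisional length group was estimated based on the secondary outcome of difference in mean" dry time. It then names the test: "The comparison will be made using a one-sided, two-sample unequal-variance t-test", at alpha 0.025, with 15 participants per product, 90% power and a detectable difference of 0.02226. The vendor supplied means only ("using estimated means (no standard deviations) from the vendor"), and an SD of 0.01 is assumed for each product, with no unit.

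The synopsis, section 6.1 and section 8.2 set up two separate randomisations. Wounds needing mesh are randomised to OptiClose Secure or Dermabond Prineo, and wounds closed with glue alone to OptiClose Rapid or Dermabond Advanced. Each has 15 v 15.

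In section 8.8.2, under Dry Time, the outcome is summarised by mean and SD and "will be compared across groups with post-hoc comparison tests". The groups and the test are not named. No omnibus test, sidedness, alpha or multiplicity rule is given, and nothing says that the comparison is made within incision length. For tubes, the same section says: "A Chi-Square test will be used to compare the observed frequencies of number of tubes between the two products".

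**The concern.** A power statement holds only for the test that will be run. Section 8.1 powers one contrast per incision length. The wording in 8.8.2 is the usual language for pairwise comparisons after an analysis of variance. Four product groups give six pairs. Only two of these (Secure v Prineo, Rapid v Advanced) are randomised; the other four set mesh wounds against glue-only wounds. A multiplicity adjustment over all six would charge the two valid contrasts for four that nobody randomised.

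The wording could also mean OptiClose v Dermabond with the lengths combined. The mesh/glue-only difference would then enter the error term unless length is in the model.

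The trial is unblinded, so an unnamed test on a product comparison could be settled after the data are seen. The tube count raises a smaller, related question: an ordered count that plausibly depends on incision length is tested as unordered categories, with no mention of length.

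**Working it through.** **Inputs from 8.1.** n = 15 per product within a length; SD 0.01 in each; one-sided alpha 0.025; 90% power. With equal SDs and sizes the Welch degrees of freedom are 28.

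**The plan's own figure.** With δ the difference in SD units and λ = δ/√(2/15), power = P(T > c), where T is noncentral t with parameter λ and c = t(0.975; 28) = 2.048. Solving for 90% gives λ = 3.359 and δ = 3.359 × 0.3651 = 1.226. The detectable difference is 1.226 × 0.01 = 0.01226, not 0.02226. At 0.02226 with SD 0.01 (2.226 SD) the Welch power is 99.996%. Two things would explain the printed value:
- an unstated shift or margin of 0.01, since 0.01226 + 0.01 = 0.02226;
- a common SD of 0.02226/1.2264 = 0.0182.

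A digit error is also possible. The documents do not say which applies.

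**Power under possible readings of 8.8.2.** These procedures are assumptions, because the plan names none. The adjusted and unadjusted pairwise tests use a one-way layout of four groups of 15 (56 df) and two-sided 5% levels.

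| Procedure | Critical value | Power at 1.226 SD | Power at 2.226 SD |
|---|---|---|---|
| Welch as in 8.1 (28 df) | 2.048 | 90.0% | 99.996% |
| Unadjusted pairwise | 2.003 | 91.0% | 99.997% |
| Tukey, four groups | 2.648 | 75.8% | 99.96% |
| Bonferroni, six contrasts | 2.735 | 73.1% | 99.95% |

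Scheffé would give 68% at 1.226 SD, and six-way Bonferroni applied to Welch tests 69%. If the SD were 0.0182, so that 0.02226 did carry 90% power, Tukey would again give 75.8% and unadjusted tests 91.0%.

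**Pooling the lengths.** If mean times differ by D within-group SDs between lengths, the unadjusted SD is √(1 + D²/4). For an assumed D = 2 this is √2 = 1.414. A difference of 0.85 SD has 89.9% power in a length-adjusted 30 v 30 analysis. Unadjusted it has 62.9% by this formula, and about 66% by direct simulation of the balanced design. By the formula, D = 1 gives about 83% and D = 3 about 43%. At 8.1's own 1.226 SD with D = 2, the unadjusted 30 v 30 test keeps 91.0%.

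**Scale.** If the unit were minutes, 0.02226 × 60 = 1.3 seconds; if seconds, 0.02 seconds. Section 6.2 checks dryness by touch every 15 seconds.

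**Tubes, illustration only.** Assume 50/30/15/5% v 15/35/30/20% of participants use 1/2/3/4 tubes, at 15 v 15 within one length. Simulated power is about 43% for chi-square and 61% for Wilcoxon.

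**The case against.** The strongest reply is that 8.8.2 is silent rather than contradictory. Section 8.1 already says which test will be used, and the groups in 8.8.2 can be read as the two products within a length. On that reading only a cross-reference is missing. Nothing states that the Welch test is dropped, that six contrasts will be run, or that lengths will be combined. This stands, and it is why the losses above are conditional.

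A reader might infer that the stated 90% power is not delivered. The documents do not support that:
- Unadjusted pairwise tests keep 91% at 1.226 SD.
- At the printed difference and SD, every procedure tried keeps at least 99.8%.
- Pooling with a 2-SD gap still gives 91% at 1.226 SD, because it uses 30 v 30. The fall to 63–66% is measured against a length-adjusted analysis that 8.1 never powered.

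The very high power at 0.02226 is no reassurance, however. It rests on an assumed SD without a unit, so it cannot make the choice of test immaterial.

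On tubes, chi-square is a legitimate test and the outcome is not powered. That lengths will be pooled is an inference from the silence on stratification. The disregard of order is on the page.

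**Conclusion.** The point holds as a failure to specify. The test that sizes the trial does not appear in the analysis of the outcome it was sized on, and the wording there admits procedures whose power at 1.226 SD runs from about 91% (unadjusted) to 76% (Tukey) and 73% (six-way Bonferroni). Those figures assume four groups of 15 with a common SD. The shortfall arises only if the unnamed procedure adjusts over all pairs.

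Separately, 8.1's 90% power and its 0.02226 do not fit its stated inputs, which give 0.01226. The pooling loss rests on an assumed gap between lengths, and the tube figures on assumed distributions; both show direction, not size. The change is worth making before analysis because it costs little and closes a choice of method in an unblinded comparison.

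**What to change.** 1. **8.8.2, Dry Time.** Replace the post-hoc wording with two pre-specified Welch t-tests as in 8.1: Secure v Prineo and Rapid v Advanced, each at one-sided alpha 0.025 with its direction stated, and each reported with the mean difference and 95% CI. Say whether the two lengths are separate questions or share one error rate; halving alpha for two tests would lower Welch power at 1.226 SD from 90% to 83%.
2. **Supportive analysis.** Add one overall product effect from a linear model with incision-length group as a factor, labelled supportive so that it does not become a third confirmatory test.
3. **8.1.** Restate the detectable difference with its unit and the basis for the SD. If the 0.01 is a margin, state it, because the 90% would then refer to a test against that margin and not against zero.
4. **8.8.2, tubes.** Replace the chi-square with a van Elteren (stratified Wilcoxon) test by incision-length group, keeping the frequency table as description.

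The cost is SAP wording and a rerun of the sample-size calculation. No extra participants, visits or data are needed.

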#### **8.8.3 Supplemental Analyses**

Not applicable.

#### **8.8.4 Adverse Device Events**

All adverse device events will be included in the analyses and report documents, including but not limited to skin irritation, redness, and itching.

## **9. SUPPORTING DOCUMENTATION AND OPERATIONAL CONSIDERATIONS**

### **9.1. Regulatory and Ethical Considerations**

#### **9.1.1. Confidentiality and Privacy**

Participant confidentiality and privacy is strictly held in trust by Medline Industries, LP. Therefore, the study protocol, documentation, data, and all other information generated will be held in strict confidence. No information concerning the study, or the data will be released to any unauthorized third party. All study data will be identified with an anonymous participant study number, and all CRFs and other documents containing data will have the participant study number and no identifiable information. One master list linking participant study numbers to participant name and other contact information will be maintained in a secure electronic database by the study (study personnel) in the event identification of a participant is necessary (e.g. due to an ADE). This is the only documentation that will link participant name and participant study number.

Study staff will ensure all source documents for data collection are completed in accordance with Good Documentation Practices (GDP) to ensure accurate interpretation of data. Data will be transferred from CRFs to a secure electronic database and analyzed with SAS® 9.4, which will allow for quality checks to identify data that appear inconsistent, incomplete, or inaccurate.

All study records will be maintained for a minimum of two years following the completion of the final round or final version of the study closeout; records will be maintained for a longer period as required by IRB or other regulations.

#### **9.1.2. Safety Oversight**

Safety oversight will consist of monitoring of visit activity, ADE and SADE by the PI, who is suitably qualified and experienced to evaluate any ADEs or SADEs. The PI will review all ADE/SADEs and make any necessary safety determinations or visit activity modification that are in the best interest of the participant as necessary. See also Section 7.0 AEs for reporting and management requirements.

#### **9.1.3. Conflict of Interest Policy**

The independence of this study from any actual or perceived influence is critical. Therefore, any actual conflict of interest of persons who have a role in the design, conduct, analysis, publication, or any aspect of this trial will be disclosed and managed.

## 9.2. Abbreviations

ADE	Adverse Device Event
UADE	Unanticipated Adverse Device Effect
SADE	Serious Adverse Device Event
ICDRG	The International Contact Dermatitis Research Group
CFR	Code of Federal Regulations
CRA	Clinical Research Associate
CRF	Case Report Form
CRO	Contract Research Organization
FDA	Food and Drug Administration
GCP	Good Clinical Practice
GDP	Good Documentation Practice
HIPAA	Health Insurance Portability and Accountability Act
ICF	Informed Consent Form
ICH	International Conference on Harmonization
IRB	Institutional Review Board
ITT	Intent to Treat
LP	Limited Partnership
PI	Principal Investigator
PSF	Participant Screening Form
SAE	Serious Adverse Device Events
SSI	Surgical Site Infection
SOA	Schedule of Activities
U.S.	United States

## 11. APPENDIX

Reaction	Definition
+?	Doubtful reaction; faint macular erythema only
+	Weak positive reaction; erythema, infiltration papules
++	Strong positive reaction; erythema, infiltration, papular, vesicles
+++	Extreme positive reaction; intense erythema, infiltration and coalescing vesicles
-	Negative reaction
IR	Irritant reaction
NT	Not tested

ID	Step-off of borders (Edges not on the same plane)	Contour irregularities (Wrinkled skin near the wound)	Margin separation (Gap between the sides)	Edge inversion (Wound not properly everted)	Excessive distortion (Swelling or infection)	Patient satisfaction score (1–10)	Operator satisfaction score (1–10)
A							
B							
C							
D							
E							

Is the overall appearance? ☐ Acceptable ☐ Not acceptable

For each wound, please answer Yes or No to each characteristic.

